## Study Protocol

This study consists of three related behavioral paradigms aiming to test sensorimotor adaptation, a correlative analysis investigating the relationship between the outcome measurements from these three experiments, and several experiments seeking to modulate these outcome measures. Here we describe Experiment 5, which used magnetoencephalographic (MEG) imaging to will noninvasively measure auditory cortical activity evoked during speech production and playback.

Experiment 5 specific Methods: In each of 3 separate sessions (order counterbalanced across participants), participants produce and listen to playback of the stimulus words *ease*, *add*, *odd*, and *ooze* (these contain the same four vowels as in Aim 1, but start without a consonant to avoid movement artifacts in MEG). We compare behavioral and neural responses induced by exposure to the perturbation field.

- *Baseline phase:* 60 productions of each word to determine each vowel's target (center of distribution in F1/F2 space) and to measure baseline variability and centering. These 240 production trials will be interleaved with 240 perception trials where participants passively listen to speech audio recorded from production trials.
- *Exposure phase, Session A:* inward-pushing perturbation field. A perturbation pushes each trial toward the vowel target measured in the baseline phase. The perturbation magnitude is 50% of the distance between the current production and the target. This effectively reduces the perceived error.
- *Exposure phase, Session B:* outward-pushing perturbation field. A perturbation pushes each trial away from the vowel target measured in the baseline phase. The perturbation magnitude is 50% of the distance between the current production and the target. This effectively increases the perceived error.
- *Exposure phase, Session C:* no perturbation is given.
- *Test phase:* Identical to baseline phase.

  

- MEG procedure: MEG data will be collected using a 306-channel, whole-head Elekta VectorView MEG system (Elekta Neuromag, Helsinki, Finland) located at the Medical College of Wisconsin, where [name] maintains an ongoing collaboration for MEG data collection. Participants will wear insert headphones and perform the speaking tasks described above.
- Data analysis and outcome measurements: Behavioral outcome variables include 1) variability across trials in F1/F2 space (Fig 2C) and 2) centering, the reduction in variability from vowel onset to vowel midpoint. The MEG analysis measures participants' auditory sensitivity to self-produced variability, as well as how this sensitivity is modulated by external manipulations to variability during the exposure phase. As in our past work, MEG sensor data from passive listening trials will be localized to its auditory cortical sources, yielding a peak source voxel in each hemisphere. From these peak voxels, the "virtual source" time-course will be estimated from the MEG sensor data in both speaking and listening trials constrained by each subject's MRI. The dependent measure is the speaking-induced suppression (SIS), defined as the z-score reduction in average M100 amplitude in the speak condition compared with the listen condition. The M100 peak is defined as the peak activity between 75 and 150 ms after stimulus onset; peaks will be confirmed by visual inspection.
- Sample size with power analysis: We planned to test 35 participants across the 3 conditions; moving to a within-subjects design, we tested 15 participants in each of our 3 conditions for a total of 45 scanning sessions. This provides a power of slightly over 0.80

at  $\alpha = 0.05$  for detecting changes in variability (0.82,  $d = 0.44$ ) and centering (0.81,  $d = 0.43$ ) observed in our behavioral data. Our previous MEG data investigating differences in within-participant SIS magnitude between different speaking conditions showed larger effects of  $d = 1.2$  (mean z-score difference of 2.8).

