## Statistical Analysis Plan

Experiment 5: Behavioral outcome variables include 1) variability across trials in F1/F2 space and 2) centering, the reduction in variability from vowel onset to vowel midpoint. The MEG analysis measures participants' auditory sensitivity to self-produced variability, as well as how this sensitivity is modulated by external manipulations to variability during the exposure phase. The dependent measure for sensitivity is the **speaking-induced suppression (SIS)**, defined as the z-score reduction in average M100 amplitude in the speak condition compared with the listen condition. The M100 peak is defined as the peak activity between 75 and 150 ms after stimulus onset; peaks will be confirmed by visual inspection. We planned to test 35 participants across the 3 conditions; moving to a within-subjects design, we tested 15 participants in each of our 3 conditions for a total of 45 scanning sessions. Given our preliminary data, this provides a power of 0.82 at  $\alpha = 0.05$  ( $d = 0.44$ ) for detecting differences in variability and a power of 0.81 at  $\alpha = 0.05$  ( $d = 0.43$ ) for detecting differences in centering. Our previous MEG data investigating differences in within-participant SIS magnitude between different speaking conditions showed larger effects of  $d = 1.2$  (mean z-score difference of 2.8).

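### Does the plan need to say how visit number enters the comparison of the three counterbalanced sessions?

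*Combined protocol and SAP*

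**What the plan says.** The Study Protocol, under Experiment 5 specific Methods, sets three sessions per participant: "In each of 3 separate sessions (order counterbalanced across participants"). Session A has the inward perturbation, Session B the outward one and Session C none. The comparison is described only in general terms: "We compare behavioral and neural responses induced by exposure to the perturbation field".

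Every session opens with a baseline phase, used among other things "to measure baseline variability and centering", and closes with a test phase described as "Identical to baseline phase".

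The MEG measure is speaking-induced suppression (SIS), a speak-versus-listen difference in M100 amplitude. It is taken from source localisation "yielding a peak source voxel in each hemisphere".

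On size, the Statistical Analysis Plan says "we tested 15 participants in each of our 3 conditions for a total of 45 scanning sessions". The protocol gives its power "for detecting changes in variability"; the Statistical Analysis Plan gives the same figure "for detecting differences in variability". Neither section names a test, a model, a contrast or the number of participants per session order.

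**The concern.** Counterbalancing removes bias from a visit effect such as practice, fatigue or growing familiarity with the scanner. It does not remove that effect from the error term. If the three conditions are compared as though visit did not exist, the balanced visit effect widens the spread of the within-participant differences and inflates the estimated standard error. With only 15 participants, and effect sizes of 0.44 and 0.43 for the behavioural outcomes, there is little precision to spare.

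The missing model also leaves two neighbouring matters open. One is whether the analysed value is the change from a session's baseline to its test phase or the test-phase value alone. The other is how the four words and two hemispheres are reduced to one value per session. A reader could therefore ask for a model with session type and visit number to be written into the plan.

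**Working it through.** **Inputs from the documents.** 15 participants, three sessions each; alpha 0.05; d = 0.44 (variability), 0.43 (centering) and 1.2 (SIS); stated power 0.82 and 0.81.

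**Assumptions.** The documents give no visit effect, variances or order counts. I take d as a standardized paired difference, a two-sided test, three orders of five participants, residual variance 0.5 per session value (so the paired difference has SD 1), and a linear drift *g* per visit in that SD.

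**1. The plan's own figures.** A two-sided paired t-test gives power 0.823 and 0.805 at n = 45, and 0.355 and 0.342 at n = 15. One-sided at n = 35 it gives 0.817 and 0.802. The stated 0.82 and 0.81 therefore do not match 15 paired differences on this reading. That is a separate question, and a visit term does not settle it: power at d = 0.44 stays near 0.37 with the term included.

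**2. Standard error without a visit term.** In the orders ABC, BCA and CAB, the position of A minus the position of C is −2, 1 and 1. The mean gap is zero, so A−C is unbiased. The variance of the gaps is 5 × (4 + 1 + 1) / 14 = 30/14 = 2.143. The ratio of standard errors is

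sqrt(1 + 2.143 × g²)

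- g = 0.1: sqrt(1.021) = 1.011
- g = 0.25: sqrt(1.134) = 1.065
- g = 0.5: sqrt(1.536) = 1.239

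**3. Error rate and power.** Simulation with 40,000 trials per setting; session-only model (28 df) against session plus visit (26 df):

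| g per visit | Type I error, no visit term | Power d = 0.44, without / with | Power d = 0.43, without / with | Power d = 1.2, without / with |
|---|---|---|---|---|
| 0 | 0.050 | 0.382 / 0.379 | 0.360 / 0.359 | 0.994 / 0.994 |
| 0.1 | 0.048 | 0.364 / 0.371 | 0.352 / 0.358 | 0.994 / 0.994 |
| 0.25 | 0.037 | 0.330 / 0.375 | 0.318 / 0.361 | 0.991 / 0.994 |
| 0.5 | 0.017 | 0.220 / 0.376 | 0.206 / 0.360 | 0.980 / 0.994 |

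With the visit term, type I error is 0.048 to 0.051. Drift of 0.25 or 0.5 per visit means 2 × 0.25 = 0.5 or 2 × 0.5 = 1.0 SD from first visit to third. Both exceed the 0.44 effect being sought.

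**4. How much drift can remain.** If the analysed value is the change from a session's baseline to its test phase, a shift common to both phases cancels. In SIS, a shift common to speaking and listening cancels as well. Only a visit effect on the change itself is left, and no section gives evidence of one.

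**5. Cost of the natural remedy.** Let the residual variances for A, B and C be 0.75, 0.25 and 0.75 (assumed). A pooled model uses their mean, 1.75/3 = 0.583, so it takes the A−C variance as 2 × 0.583 = 1.167 when it is 0.75 + 0.75 = 1.5. The visit-adjusted pooled model then has an A−C type I error of 0.082 to 0.085. A plain paired t-test without visit gives 0.048, 0.048 and 0.042 at g = 0, 0.1 and 0.25. The inflation comes from pooling the variance, not from the visit term as such. A paired comparison stratified by order avoids both problems (0.049 to 0.052), but it has 12 df and power 0.348 at d = 0.44, against 0.375 for the visit-adjusted model.

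**6. Order counts.** Fifteen is not a multiple of six, yet positions can still balance over six orders: 3 × 3 + 3 × 2 = 15, with three participants per order in one Latin square and two in the other. One uneven six-order allocation, analysed without visit, gave a B−C bias of about −0.03 at g = 0.25 and −0.07 at g = 0.5. That arises only if positions were not in fact balanced.

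**The case for a change.** The best case for a change is that stating the model costs a few sentences and no data. With no visit effect, the visit term lowers power at d = 0.44 only from 0.377 to 0.375. The cancellation in a change score is also an inference. The protocol writes of changes and the Statistical Analysis Plan of differences, and neither defines the analysed value as test phase minus baseline. Treating words or hemispheres as independent rows could also inflate false positives: at assumed within-session correlations of 0.1 to 0.5, type I error is 0.062 to 0.137 with two rows per session and 0.090 to 0.260 with four.

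Part of this stands. The analysis description is thin, and a report should give the summary value, the contrasts and the number of participants per order. But the row-level figures describe an analysis that neither section proposes, and they say nothing about visit number. The plan contains no rule that excludes visit; it is silent, and silence on one covariate in a balanced design is a gap that an analyst can fill sensibly. Both sections also say that the participants were tested, so a sentence added now would not have the standing of a choice made in advance.

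**Conclusion.** The silence is real, but it does not call for a change. With balanced positions, omitting visit leaves A−C and B−C unbiased. With equal variances, the error is on the conservative side.

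The cost is a 1% larger standard error at 0.1 SD of drift per visit, 6% at 0.25 and 24% at 0.5. For SIS, power stays at 0.98 or above throughout that range. The larger losses rest on an assumed visit effect on the within-session change for which the documents give no support.

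The model one would naturally write in is not clearly better. Under the unequal variances assumed above, it exchanges a small conservative loss for a false-positive rate of 0.082 to 0.085. The choice between paired differences and a visit-adjusted model is a fair trade-off that the analyst can make and report.

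This rests on balanced positions, on d being a standardized paired difference, and on one value per participant per session. It does not address carry-over between session types, which a visit term would not remove either, or the basis of the stated power.

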## Statistical Analysis Plan

Experiment 5: Behavioral outcome variables include 1) variability across trials in F1/F2 space and 2) centering, the reduction in variability from vowel onset to vowel midpoint. The MEG analysis measures participants' auditory sensitivity to self-produced variability, as well as how this sensitivity is modulated by external manipulations to variability during the exposure phase. The dependent measure for sensitivity is the **speaking-induced suppression (SIS)**, defined as the z-score reduction in average M100 amplitude in the speak condition compared with the listen condition. The M100 peak is defined as the peak activity between 75 and 150 ms after stimulus onset; peaks will be confirmed by visual inspection. We planned to test 35 participants across the 3 conditions; moving to a within-subjects design, we tested 15 participants in each of our 3 conditions for a total of 45 scanning sessions. Given our preliminary data, this provides a power of 0.82 at  $\alpha = 0.05$  ( $d = 0.44$ ) for detecting differences in variability and a power of 0.81 at  $\alpha = 0.05$  ( $d = 0.43$ ) for detecting differences in centering. Our previous MEG data investigating differences in within-participant SIS magnitude between different speaking conditions showed larger effects of  $d = 1.2$  (mean z-score difference of 2.8).

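### Does centering need a formula and an onset-adjusted analysis to keep it separate from variability?

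*Combined protocol and SAP*

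**What the plan says.** Both parts of the combined document name the same two behavioural outcomes. The Study Protocol, under data analysis and outcome measurements, lists "variability across trials in F1/F2 space (Fig 2C) and 2) centering", with a pointer to a figure that is not reproduced in the text available. The Statistical Analysis Plan repeats the sentence without the pointer: "variability across trials in F1/F2 space and 2) centering". Centering is then described as "centering, the reduction in variability from vowel onset to vowel midpoint".

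The baseline phase yields "60 productions of each word to determine each vowel's target" and serves "to measure baseline variability and centering"; the test phase repeats it. Sessions A and B apply the inward and outward perturbation fields, and Session C applies none.

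The two outcomes are powered separately, at d = 0.44 (power 0.82) for variability and d = 0.43 (power 0.81) for centering. The protocol says these effects were "observed in our behavioral data". Neither part gives a formula for centering, a dispersion statistic, or an analysis of centering that conditions on onset variability.

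**The concern.** Write O for variability at vowel onset and M for variability at midpoint. If centering is O − M, and outcome 1 is measured at onset or at midpoint, outcome 1 is one of the two terms of outcome 2. The sessions are designed to act on perceived error, and the power statement expects variability to change. A session effect on centering might then be read as stronger or weaker within-vowel correction when only the starting spread had moved. Equally, a real change in correction could be masked by an onset change in the other direction. Session C removes drift common to all sessions, but not an onset change specific to A or B. At stake is how the centering result is interpreted, not whether O − M is computed correctly.

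**Working it through.** **The plan's own figures.** A two-sided paired t-test at α = 0.05 with n = 45 gives power 0.823 for d = 0.44 and 0.805 for d = 0.43, matching 0.82 and 0.81. A one-sided test with n = 35 also matches (0.818 and 0.802). With n = 15 the two-sided values are 0.355 and 0.342; that mismatch is a separate matter. Because d has no units, the match says nothing about whether centering was absolute or proportional.

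**The coupling by arithmetic (assumed units).** Take O = 50 and M = 40, so centering is 10 and the share corrected is 10/50 = 20%. If onset rises to 55 with the same share corrected, M = 0.8 × 55 = 44 and centering is 11: up 10% in absolute terms, unchanged as a share. If instead a fixed amount of 10 is corrected, M = 45 and centering stays at 10.

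**Its size at the planned effect.** Assume the variability effect applies at onset, which the documents do not state: a net onset change of 2.2 units with SD 5, so d = 2.2/5 = 0.44. With correction unchanged, the shift in O − M is:

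| Correction rule (assumed) | Shift in O − M |
|---|---|
| Fixed share of 20% | 0.20 × 2.2 = 0.44 |
| Half share, half fixed amount | 0.10 × 2.2 = 0.22 |
| Fixed amount | 0 |

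The largest value is 0.44/10, about 4% of baseline centering. Nothing in the documents selects among the rules.

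**The remedy, without measurement error.** Regress net midpoint change on net onset change and test the intercept. In simulations of 15 participants with onset measured exactly, the adjusted estimate stays within 0.01 of zero when correction is unchanged.

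**The remedy, with measurement error in onset.** Let the observed onset change have reliability R. Under the fixed-share rule the true slope is 0.8, and the fitted slope is attenuated to 0.8R. The fitted intercept is then

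0.8 × 2.2 − 0.8R × 2.2 = 1.76 × (1 − R),

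which is a spurious change in centering of −1.76 × (1 − R).

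| R (assumed) | Shift in O − M | Adjusted estimate, centering sign |
|---|---|---|
| 1.00 | +0.44 | 0 |
| 0.75 | +0.44 | −0.44 |
| 0.50 | +0.44 | −0.88 |

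The two biases are equal in size when 1.76 × (1 − R) = 0.44, that is at R = 0.75; below that the adjusted analysis is the more biased. Simulation of 40,000 studies of 15 participants agrees with these means to within about 0.01. At R = 0.5, with midpoint noise SD 1.41 and the SD of 5 taken as that of the observed change, the nominal 5% test rejects in 21% of studies for the adjusted estimate and 7% for O − M. The documents give no reliability for onset variability. Each value is a dispersion estimated from 60 productions per word per phase, so some error is certain.

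**What readers can recover.** Variability is itself a reported outcome. If it is taken at onset or midpoint on the same scale as O − M, the other term follows by subtraction: onset 50 and centering 10 give midpoint 40 and a group-level share of 20%. So in the case where the overlap is most direct, the proportional reading can be derived.

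**The case for a change.** The best case for a change is that the same paragraph of the Statistical Analysis Plan specifies speaking-induced suppression with a scale, a contrast and a time window, while the behavioural outcomes have none of these. A formula must already exist, so writing it down would cost a few lines. An onset-adjusted analysis labelled as supportive would leave the main outcome and its power alone. Under a fixed share it would also guard against real misreading: with a true increase of 0.83 units, O − M would average 1.30 if onset rose and 0.35 if it fell, while the adjusted estimate, with onset measured exactly, stays between 0.80 and 0.84.

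Part of this stands. The text is thinner for these outcomes than for the MEG measure, and a report that states the formula and time points and shows onset and midpoint variability by phase and session would be easier to read. That is a matter of reporting and alters no planned result. The time-point gap may also be only apparent, since the figure cited in the protocol may supply it.

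The case for the regression is weaker. Its advantage rests on error-free onset values. It also conditions on a quantity that exposure may itself change, and so answers a different question from the one the plan poses. The reliability figures used against it are assumed too, so they do not show that O − M is better; they show that neither analysis dominates.

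**Conclusion.** The concern describes the text correctly but does not call for a change. The plan defines centering as a reduction in variability and claims neither a correction share nor independence from variability; onset minus midpoint is a valid estimate of that reduction. The missing formula, scale and time points are a gap that analysts can fill sensibly from the measure behind the observed effects. The coupling with onset variability is genuine but of unknown size: 0 to 0.44 units on a baseline of 10 in simple models that assume the correction rule, a 20% share at baseline and an onset effect of d = 0.44. The onset-adjusted regression would exchange that possible bias for one in the opposite direction, equal in size at onset reliability 0.75 and twice as large at 0.5, and would change the estimand. That is a trade-off with no clear gain at 15 participants.

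### The stated behavioural power of 0.82 and 0.81 does not follow from 15 participants: a paired t-test with d on the SD of differences gives about 0.36 and 0.34, and the inputs that could close the gap are not stated

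*Combined protocol and SAP*

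**What the plan says.** The Study Protocol (Experiment 5 specific Methods) describes a crossover of three sessions: "In each of 3 separate sessions (order counterbalanced across participants"). Its sample size paragraph explains that the target changed: "moving to a within-subjects design, we tested 15 participants in each of our 3 conditions for a total of 45 scanning sessions". It continues: "This provides a power of slightly over 0.80" at alpha 0.05, with 0.82 for variability (d = 0.44) and 0.81 for centering (d = 0.43).

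The Statistical Analysis Plan repeats the claim. It recalls the earlier target ("We planned to test 35 participants across the 3 conditions"), gives the same 15 participants per condition, and then states: "45 scanning sessions. Given our preliminary data, this provides a power of 0.82 at" alpha 0.05, followed by 0.81 for centering.

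Neither section names the test, its sidedness, the SD by which d is scaled, or the correlation between repeated measures. The powered contrast is not identified either. The protocol has "for detecting changes in variability" and the plan has "for detecting differences in variability". These could mean baseline-to-test change within a session or a difference between sessions.

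**The concern.** In a within-subjects design the independent unit is the person. Any contrast between Sessions A, B and C, or between baseline and test within a session, rests on 15 independent participants. Measuring four vowels per session gives more data points but no more people. Power above 0.80 for a standardised effect of about 0.44 is not what 15 participants would usually give, and the sample size text points to the 15-participant, 45-session design as the source of that power.

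Variability and centering are the two named behavioural outcomes. On the stated figures, the chance of missing the assumed effect is 18% (1 − 0.82) or 19% (1 − 0.81), so a reader could take a non-significant result as fair evidence against an effect. If the true power is much lower, that reading is not justified.

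**Working it through.** **Inputs from the documents.** n = 15 participants, 3 sessions each, 45 sessions; earlier target 35; alpha = 0.05 (sidedness not given); d = 0.44 (variability) and 0.43 (centering), standardiser not given; stated power 0.82 and 0.81.

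**Formula.** Paired t-test: noncentral t with df = n − 1 and noncentrality d√n, where d is the mean difference divided by the SD of differences (an assumption, since the plan does not say).

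**Step 1: which n gives the plan's figures?**

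| n | sides | d√n for 0.44; 0.43 | power for 0.44; 0.43 |
|---|---|---|---|
| 45 | two | 2.95; 2.88 | 0.823; 0.805 |
| 45 | one | 2.95; 2.88 | 0.896; 0.884 |
| 35 | two | 2.60; 2.54 | 0.715; 0.696 |
| 35 | one | 2.60; 2.54 | 0.818; 0.802 |
| 15 | two | 1.70; 1.67 | 0.355; 0.342 |
| 15 | one | 1.70; 1.67 | 0.491; 0.476 |

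Taking d as exactly 0.44 and 0.43, and searching n from 3 to 199, n = 45 two-sided is the only n that rounds to both 0.82 and 0.81. No single n does so one-sided (0.82 at n = 35, 0.81 at n = 36). This is a numerical match, not proof of how the figures were obtained. A simulation of 300,000 runs at n = 15 agrees with the formula: 0.357 and 0.342 two-sided, 0.492 and 0.476 one-sided.

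**Step 2: what would make 15 participants enough in a paired t-test?** Suppose d is on the raw SD and r is the correlation between conditions. The paired effect is then d / √(2(1 − r)). Two-sided power at n = 15:

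| r | 0 | 0.3 | 0.5 | 0.7 | 0.8 | 0.85 |
|---|---|---|---|---|---|---|
| d = 0.44 | 0.202 | 0.269 | 0.355 | 0.535 | 0.708 | 0.824 |
| d = 0.43 | 0.195 | 0.259 | 0.342 | 0.517 | 0.688 | 0.807 |

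The stated power is reached at r = 0.848 and 0.851 two-sided, or 0.800 and 0.803 one-sided.

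**Step 3: three-level repeated-measures ANOVA, n = 15.** Noncentrality is f² × 15 × 3 / (1 − r), with 2 and 28 degrees of freedom. With f = d/2, power is 0.407 and 0.391 at r = 0.5 and 0.622 and 0.601 at r = 0.7. The stated figures need r of about 0.81. If the quoted values were entered as Cohen's f rather than d, r of about 0.23 to 0.24 would be enough.

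**Step 4: what 15 participants can detect (d on the SD of differences).**
- 80% power needs d = 0.778 two-sided or 0.675 one-sided.
- The smallest observed d that reaches significance is 2.145/√15 = 0.554 two-sided or 1.761/√15 = 0.455 one-sided.
- An observed d of 0.44 would have an approximate 95% interval of 0.44 ± 0.554, that is −0.11 to 0.99.
- Two-sided 80% power at the plan's d needs 43 participants (0.44) or 45 (0.43); one-sided, 34 or 35.

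**Step 5: SIS, for scope.** At d = 1.2 on the SD of differences and n = 15, two-sided power is 0.991.

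**The case against.** The strongest reply is that 0.36 and 0.34 are conditional. With no test or standardiser named, the stated power cannot be shown to be impossible. A repeated-measures ANOVA is a natural analysis for three within-participant conditions, and Steps 2 and 3 show routes by which 15 participants reach about 0.82 and 0.81. That is correct, and a sponsor who used such a route should be free to say so. It does not rescue the statement as written. Each route depends on a correlation the plan does not give, and the one that needs only a modest correlation treats a value labelled d as a different effect measure.

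A second reply is that the match at 45 should not carry much weight. The effect sizes are rounded. At n = 35 one-sided, d between 0.44 and 0.445 gives 0.818 to 0.825, and d between about 0.4325 and 0.435 gives 0.806 to 0.810. Carry-over from the earlier target of 35 is therefore also plausible. This stands: the source of the figures is open. The conclusion does not depend on it, because neither calculation describes 15 participants.

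Two smaller points also stand. The difference between changes and differences is slight by itself; it matters only because the contrast is not defined elsewhere. The reassurance on SIS assumes that d = 1.2, taken from earlier data on other speaking conditions, carries over to this perturbation contrast.

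**Conclusion.** The concern holds. From the stated n and d, a paired t-test with d on the SD of differences has power 0.36 and 0.34 two-sided, or 0.49 and 0.48 one-sided, against the stated 0.82 and 0.81. The risk of missing the assumed effect is then about 65% two-sided (1 − 0.355 = 0.645; 1 − 0.342 = 0.658) or 51% to 52% one-sided. An observed effect exactly as large as assumed would not be significant under either sidedness.

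These figures rest on the standardiser assumption. With d on the raw SD, a paired t-test reaches the stated power only at a correlation of about 0.85 two-sided or 0.80 one-sided. The power is therefore unsupported as written. The finding is limited to variability and centering; SIS is adequately powered if its assumed effect applies.

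**What to change.** In both the Study Protocol sample size paragraph and the Statistical Analysis Plan, restate the behavioural power with the participant (n = 15) as the unit of replication. First name the contrast (using the same term in both places), the test, its sidedness, the standardiser of d and, where it enters, the within-participant correlation and its source. Then give the power that follows. If the analysis is a two-sided paired test with d on the SD of differences, suitable text is:

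> With 15 participants, a two-sided paired t-test at alpha 0.05 has power of about 0.36 for variability (d = 0.44) and 0.34 for centering (d = 0.43), where d is scaled to the SD of within-participant differences. Power of 80% requires d of about 0.78.

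If a one-sided test, a raw-SD d with a correlation, or a repeated-measures ANOVA was used, state those inputs and give the power they produce instead. Add that the behavioural effects will be reported with 95% confidence intervals, and that a non-significant result will not be read as evidence of no effect on the strength of the 0.82 and 0.81 figures.

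The cost is wording, plus a less favourable power figure unless the missing inputs can be supplied. No further participants are needed and the SIS outcome is unchanged.
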